## **METHODS**

**Study design:** We propose to conduct a pilot non-randomized-controlled trial to evaluate the impact of “Tomando control de su salud”, an evidenced-based intervention for chronic disease self-management, in the quality of life of patients living with Long-COVID in Puerto Rico.

**Participant selection:** We will invite patients from our cohort study during the 12-month follow-up call. All participants identified with conditions associated with Long COVID or chronic diseases will be invited to participate. These are the inclusion and exclusion criteria:

Inclusion criteria:

- 1) Adult patients 21 years or older
- 2) Participant of PR-COAS cohort that completed the last interview (12-month-follow-up) and authorized to be contacted for further studies.
- 3) Having at least one chronic condition (excluding cancer) diagnosed by a physician or healthcare provider.
- 4) Ability to attend weekly sessions (applicable to intervention group).

Exclusion criteria

- 1) Any clinical or cognitive impairment that limits the participant's ability to decide to participate in the study or complete the interviews.
- 2) Presence of a life threatening or extreme medical condition.

- 3) Planning to move out of the municipality within the next year.

**Sample size determination:** The primary goal of this study is to pilot the potential implementation of this intervention for Long COVID patients. We are therefore not powering for a definitive assessment of the difference between any two groups. However, we expect the preliminary data from this study to provide adequate pilot data from which we will be able to determine the required sample size for a larger scale study. The sample selected will provide an estimate of the effect size and thereby allow preliminary evaluation of the clinical utility associated with the intervention.

**Sampling strategy:** Participants with Long-COVID and chronic diseases that agree to participate in the intervention will be allocated into one of the study intervention groups that will participate in the “Tomando Control de su Salud” workshops. Those not interested in participating in the intervention will receive general information about chronic disease management available at the CDC website in Spanish, by email, regular postal mail or in person, in addition to their regular health care and will be asked to answer the post questionnaires approximately 3 months after the last interview of the PR-COAS cohort. With an estimated participation rate of about 25 – 30% we expect to identify between 20-25 participants with Long-COVID with at least one-chronic condition. We estimate that about half will be interested in receiving the intervention; therefore, we expect to have about 20-25 participants in the intervention arm divided into two or three workshops of 8 – 12 participants based on the number of patients recruited and about 30-40 participants in the general care group. Figure 2 summarizes the expected recruitment and procedures.

**Proposed intervention:** “Tomando control de su salud” (Spanish Chronic Disease Self-Management)  is a culturally appropriate program developed in Spanish to support Hispanics

patients to build confidence in their ability to manage their health. This intervention was developed by Lorig et al. at Stanford University and has been widely used by the Puerto Rico Department of Health since it is recommended by the CDC as an evidenced-based intervention for chronic disease management.

[figure not shown]

Figure 2: Summary of study recruitment and procedures, PR COAS\_TCS

The intervention consists of small group workshops with 8 to 15 participants lead by two certified trainers, offered virtually or face-to-face (at the EHSRC Office of Clinical and Community Health Research located at the Hospital UPR in Carolina) for 2 1/2 hours once per week for six-week period open to Spanish-speakers with any physical or mental chronic condition or multiple chronic conditions. As part of the intervention, a pre and post TCS assessment will be collected.

Topics included in the training are:

- 1) Healthy eating
- 2) Appropriate exercise for maintaining and improving strength, flexibility, and endurance
- 3) Managing depression
- 4) Appropriate use of medications
- 5) Communicating effectively with family, friends, and health professionals
- 6) Relaxation techniques
- 7) Appropriate use of the health care system
- 8) How to evaluate new treatments
- 9) Better breathing
- 10) Action-planning, problem-solving, and decision-making skills.

Our research group has experience with this intervention including the successful implementation of the program among patients with diabetes and hypertension living in a low-income community in Puerto Rico. The intervention will be implemented in collaboration with Puerto Rico Department of Health and the participating FQHC centers.

**Outcome measures, study variables and instruments:** We will use instruments and adapted questions from standardized questionnaires developed and currently used by the Centers for Disease Control, the National Institutes of Health, the World Health Organization, or clinical centers to develop the interviews to collect data related the study variables. We will use questionnaires that are available for public use, and the questions will be used as stated or modified if needed. The use of these standardized questionnaires will allow us to standardize the data collection process and eventually compare the experiences in Puerto Rico with those in other locations. The Table 1 summarizes the data to be collected and instruments.

The last interview of the cohort study (PR-COAS) in which the participants will be identified, which collect information on general aspects of self-care of chronic diseases, healthcare utilization, vaccination status, lifestyles modifications, and health-related quality of life among others, will be used as baseline for the purposes of this study. In addition, a follow up interview will be coordinated one month after completing TCS for the intervention group and approximately 3 months after the last interview of the cohort study for the control group. The following indicators will be collected: Health care services utilization (primary care, emergency room and hospitalizations), compliance with prescribed medications, risk behaviors (such as smoking, physical activity, alcohol use), nutritional awareness, self-efficacy for disease management based on the level of confidence) and quality of life. The standard data collected by the PRDOH for this intervention (*Formulario 1: Formulario Inicial, Preprueba, and Formulario 2: Formulario Final, Post-Prueba & Evaluación, Rev. Enero 2022*) will also be used for analysis. The Form 1 is a self-administered questionnaire of 28 closed-ended questions that collects TCS participants' sociodemographic and contact information (name, municipality of residence, marital status, education, age, sex, medical plan, email), general information on diagnosed health chronic conditions, COVID-19 vaccination, level of confidence in managing chronic conditions, general health, use of health services, and lifestyles (e.g. consumption of vegetables, fruits and alcoholic beverages, physical activity and whether or not you smoke). The Form 2 is a 40-question self-administered questionnaire that mainly collects general information about the lifestyles of TCS workshop participants (consumption of vegetables, fruits and alcoholic beverages, physical activity and whether or not they smoke), general health status, level of confidence in managing health chronic conditions, utilization of health services, attendance, evaluation and experience in TCS workshop.

The impact of health-related quality of life will be assessed using the following scales:

- EQ-5D-5L (Spanish version), which includes five dimensions: mobility, self-care, daily activities, pain or discomfort, and anxiety or depression.
- Fatigue (NIH PROMIS® Neuro-QoL Item Bank v1.0, Short Form, Spanish version)
- Post-COVID-19 Functional Status Scale (PCFS, Spanish version) - It is an ordinal tool that focuses on relevant aspects of daily life during follow-up after the COVID-19 infection. PCFS includes the entire range of functional outcomes by focusing on limitations (if any) in usual duties/activities either at home or at work/study, as well as changes in lifestyle.
- Anxiety (GAD-7, Spanish version) - It is a validated one-dimensional 7-item questionnaire for generalized anxiety disorder assessment, as listed in the DSM-IV.

In general terms, chronic diseases self-management and auto-efficacy will be assessed through the following scales:

- Self-Care of Chronic Illness Inventory (SC-CII v4.c, Spanish version) – It is an internationally generic measure used to assess self-care in chronic diseases, and it is based on the Theory of Self-Care of Chronic Illness. SC-CII comprises four scales: self-care maintenance (Section A), self-care monitoring (Section B), self-care management (Section C), and self-care confidence (Section D). For our study, we will just use the first three sections of this instrument.
- NIH PROMIS® 4-item Short Forms v1.0, 4a - Self-Efficacy for Managing Chronic Conditions, which is a multidimensional categorical model to estimate individual's self-efficacy for managing their health chronic diseases through the following five behavioral domains:
  - Self-Efficacy for Managing Daily Activities
  - Self-Efficacy for Managing Emotions

- Self-Efficacy for Managing Medications and Treatments
- Self-Efficacy for Managing Social Interactions
- Self-Efficacy for Managing Symptoms 

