### Specific Aim 1:

To evaluate the impact of an evidenced-based intervention for chronic disease self-management in the health-related quality of life (HRQoL) of patients living with Long-COVID in Puerto Rico. To do this we will evaluate the implementation of **“Tomando control de su salud”** (TCS) among patients with Long COVID and chronic diseases participating in the PR-COAS cohort study, and the changes (if any) in data related to HRQoL measures, included data from the baseline and follow up interviews, before and after this implementation. “Tomando control de su salud” is an evidenced based intervention in Spanish and a culturally appropriate version similar to the Chronic Disease Self-Management program of the Centers for Disease Control and Prevention (CDC) aimed to improve disease management skills, including decision-making, problem solving, and action planning among patients with at least one chronic condition.

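### The listed eligibility criteria do not require Long COVID, which conflicts with both aims and with the Sampling strategy paragraph, so people with a chronic disease but no Long COVID may be enrolled in either group

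*Combined protocol and SAP*

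**What the plan says.** Aim 1 is to evaluate the programme's impact "in the health-related quality of life (HRQoL) of patients living with Long-COVID in Puerto Rico", and it describes implementation "among patients with Long COVID and chronic diseases participating in the PR-COAS cohort study, and the changes (if any) in data related to HRQoL measures". Aim 2 and the study design sentence also name patients with Long COVID.

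Participant selection, under METHODS, opens differently: "All participants identified with conditions associated with Long COVID or chronic diseases will be invited to participate". The inclusion criteria that follow are:

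1. a minimum age of 21
2. membership of PR-COAS, with the 12-month interview done and permission given for later contact
3. a chronic disease, worded as "Having at least one chronic condition (excluding cancer) diagnosed by a physician or healthcare provider"
4. being able to attend the weekly sessions, for the intervention group only

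The three exclusion criteria cover impairment, life-threatening or extreme illness, and planned relocation. Long COVID appears in none of the seven.

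The Sampling strategy paragraph returns to the narrower population: "Participants with Long-COVID and chronic diseases that agree to participate in the intervention will be allocated into one of the study intervention groups". The comparison group is those not interested in the intervention. Long COVID is not restated for them.

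**The concern.** Recruiters screen against the numbered list. Someone with diabetes who has recovered fully from COVID-19 meets every listed criterion and matches the invitation sentence. Such a person does not belong to the population named in the aims or in the Sampling strategy paragraph. The plan therefore carries two rules, and staff who follow the listed one commit no deviation from it.

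Two things are at stake. First, a conclusion about patients living with Long COVID would rest on a group that includes people without it, and the same would hold for the effect size meant to inform a larger study. Second, groups form by self-selection. If joiners and decliners differ in how many have Long COVID, the comparison of change scores could be biased. Nothing later in the plan repairs this: Table 1 lists no Long COVID status item, and Data analysis defines no Long COVID analysis set, subgroup or covariate.

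**Working it through.** **1. The rules side by side.**

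| Place | Population described |
|---|---|
| Specific Aim 1 | Long COVID and chronic diseases |
| Specific Aim 2 | Long COVID (and chronic diseases in its second sentence) |
| Invitation sentence | Long COVID-associated conditions *or* chronic diseases |
| Listed criteria | At least one chronic condition; Long COVID not mentioned |
| Sampling strategy, workshops | Long COVID and chronic diseases |
| Sampling strategy, comparison group | Those not interested; Long COVID not restated |

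Criterion 3 applies to everyone, so the gap runs one way: it admits people with a chronic disease and no Long COVID.

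**2. Does cohort membership supply Long COVID?** No. The Background says PR-COAS enrolled people with laboratory-confirmed infection. Its prevalence figure reproduces: 191/256 = 74.6%. The remainder is 65/256 = 25.4% without Long COVID.

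**3. Share without Long COVID among people with a chronic condition.** Criterion 3 narrows the pool, so 25.4% is not the relevant share. Let c be the proportion of the cohort with a chronic condition, and p1 and p0 the Long COVID prevalence with and without one. Solve

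- c·p1 + (1 − c)·p0 = 191/256
- [p1/(1 − p1)] / [p0/(1 − p0)] = OR

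Inputs: OR 3.38 with 95% CI 1.62–7.04 (Background). The documents do not give c for this cohort, so 50–80% is an assumption. The earlier record review reports almost 50% among confirmed cases, but in a different sample.

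Share without Long COVID (1 − p1):

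| c | OR 3.38 | OR 1.62 | OR 7.04 |
|---|---|---|---|
| 0.5 | 14.4% | 20.9% | 9.2% |
| 0.6 | 16.1% | 21.7% | 11.1% |
| 0.7 | 18.0% | 22.5% | 13.7% |
| 0.8 | 20.2% | 23.4% | 17.0% |

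Check for c = 0.5 and OR 3.38: p1 = 0.8555 and p0 = 0.6366. Their average is 0.746, and (0.8555/0.1445)/(0.6366/0.3634) = 3.38.

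**4. In participants.** The planned groups are 20–25 and 30–40, so 50–65 in total. If only the listed criteria were applied:

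- all participants: 0.144 × 50 = 7.2 to 0.202 × 65 = 13.1
- intervention group: 0.144 × 20 = 2.9 to 0.202 × 25 = 5.1

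**5. Dilution.** If a fraction q of the intervention group has no effect on an outcome, the average effect is (1 − q) times the effect in the rest. With q = 14–20%, that outcome's estimate shrinks by 14–20%. This applies only where the effect without Long COVID really is zero.

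**The case against.** The strongest reply is that the Sampling strategy paragraph states who is allocated, and those people have Long COVID and chronic diseases. Its forecast is also worded in terms of people with both, and the decliners appear to come from the same pool. A broad invitation followed by narrower selection is not an error in itself. This stands as evidence of intent, and it rules out one tempting inference: that the trial *will* enrol people without Long COVID. The documents support only that the listed criteria permit it. The reply does not remove the conflict, because the paragraph adds no criterion, case definition or time of assessment.

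A reader might also infer that a quarter of participants would lack Long COVID. The 25.4% describes the whole cohort, before criterion 3 is applied.

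A third tempting inference is that every effect estimate would shrink by the share without Long COVID. The programme is open to people with any chronic condition. The EQ-5D-5L, GAD-7, self-care inventory, self-efficacy forms and fatigue short form are generic, and may respond equally without Long COVID. The dilution argument is strongest for the Post-COVID-19 Functional Status Scale, and even that measures function after infection rather than Long COVID alone.

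Finally, this is an unpowered pilot focused on estimation. That lowers the severity, but a pilot's estimate still has to belong to a defined population.

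**Conclusion.** The concern holds as a conflict between stated rules. The listed criteria and the *or* in the invitation permit enrolment, in either group, of people with a chronic disease but no Long COVID, while both aims and the Sampling strategy paragraph describe people who have it. If the list alone were applied, roughly 14–20% of those eligible would lack Long COVID, or about 9–23% over the odds ratio's confidence interval.

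These figures are indicative. They rest on a preliminary prevalence not measured at the 12-month interview, an odds ratio adjusted for age, sex and severity but used as crude, and an assumed chronic-condition share of 50–80%. The documents do not give Long COVID status at month 12, so the true share could lie outside the range.

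The main consequence is a mismatch between the conclusion and the people enrolled. A differing Long COVID mix between joiners and decliners is possible but not shown. Severity: should be fixed, given that this is a pilot.

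**What to change.** Reconcile Participant selection with Sampling strategy in one of two ways.

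- **If the aims stand:** add Long COVID to the inclusion criteria for both groups, stating the sponsor's case definition and the time at which it is assessed, and change *or* to *and* in the invitation sentence. The definition has to be written out, because the documents do not set out the one used in PR-COAS.
- **If the wider population is intended:** restate the aims accordingly, record Long COVID status at baseline, and prespecify participants with Long COVID at baseline as the analysis set for any conclusion about Long COVID.

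The cost is a short amendment and a somewhat smaller eligible pool or analysis set. The Background says that persistent or new symptoms were collected at PR-COAS interviews up to month 12, so little new data collection may be needed. The sponsor should confirm this, since neither the description of the baseline interview nor Table 1 lists a Long COVID item.

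### Ability to attend weekly sessions is required of the intervention arm only and never recorded in controls, adding an eligibility asymmetry to a self-selected, unadjusted comparison

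*Combined protocol and SAP*

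**What the plan says.** The study is described under Study design as a "pilot non-randomized-controlled trial to evaluate the impact of" the self-management programme (TCS). Under Participant selection, inclusion criterion 4 is "Ability to attend weekly sessions (applicable to intervention group". The other inclusion criteria and all three exclusions carry no such restriction to one arm.

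Sampling strategy forms the arms by choice. Participants "that agree to participate in the intervention will be allocated into one of the study intervention groups", while "Those not interested in participating in the intervention will receive general information about chronic disease management" and a later questionnaire. The text does not say where a person goes who is interested but cannot attend. It does not provide for recording ability to attend or the reason for declining.

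Workshops run 2.5 hours a week for six weeks, "offered virtually or face-to-face" (Proposed intervention).

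Data analysis plans estimates and 95% confidence intervals for the change in each group and for the difference in change between groups, with rank tests on the change scores. Baseline characteristics are to be compared between groups. No covariate adjustment, matching, weighting or restriction is mentioned.

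**The concern.** An entry condition that applies to one arm makes the arms differ by rule, over and above any difference from choice. Attending means 6 × 2.5 = 15 hours of sessions, whereas control follow-up is described as one interview. The condition also lies close to the outcomes: the quality-of-life set includes fatigue, post-COVID functional status, and the EQ-5D-5L mobility and daily-activity dimensions. Someone limited by moderate fatigue, disability, working hours or transport can be a control but not a workshop participant.

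If ability to attend is related to how these scores change over about three months, the between-group difference mixes the programme's effect with a difference between kinds of people. That matters even in a pilot, because Sample size determination says the data will be used to size a larger study and to judge clinical utility. Since ability to attend is not recorded in controls, the final dataset could not show directly whether this happened.

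**Working it through.** **1. Who can be in each arm under the written rules**

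- Interested and able: TCS.
- Interested but unable: barred from TCS by criterion 4; not described as a control by Sampling strategy; destination not stated in the text.
- Not interested but able: control.
- Not interested and unable: control.

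People unable to attend are thus absent from TCS by rule and permitted among controls. How many there would be is not stated.

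**2. The plan's own figures**

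The plan gives no figure for this bias and no power calculation. Its only relevant figures are the expected arm sizes, 20–25 (TCS) and 30–40 (general care). These do not follow from the stated steps: "With an estimated participation rate of about 25 – 30% we expect to identify between 20-25 participants with Long-COVID", of whom about half would want the intervention, gives 20 × 0.5 = 10 to 25 × 0.5 = 12.5. That mismatch is a separate matter. I take the arm sizes as stated and use 22 and 35, near the middle of each range.

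**3. Precision of the between-group difference**

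In SDs of the change score, assuming equal SDs, no dropout and no workshop clustering: half-width = 1.96 × √(1/n₁ + 1/n₀).

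- 22 v 35: 1.96 × √(0.0455 + 0.0286) = 0.533
- 20 v 30: 0.566
- 25 v 40: 0.500

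**4. Possible bias**

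Let f be the share of controls unable to attend and d the gap in mean change between unable and able controls, in SDs. Relative to a comparison with able controls only, the shift is f × d. Neither input is in the documents; both are assumptions.

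- f = 20%, d = 0.2: 0.04 SD
- f = 40%, d = 0.3: 0.12 SD
- f = 60%, d = 0.5: 0.30 SD

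A lower range for f gives 0.10 × 0.2 = 0.02 SD to 0.50 × 0.5 = 0.25 SD. The sign follows that of d. If unable controls do worse over time, TCS is favoured. If they start lower and regress toward the mean, or are busy because they are fitter and working, the shift could go against TCS.

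**5. What a shift of 0.12 SD would do to later planning**

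Assume a true effect of 0.30 SD, 80% power and two-sided 5%. Then n per arm = 2 × (1.96 + 0.84)² / effect², with numerator about 15.70.

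- 0.30: 15.70 / 0.0900 ≈ 175
- 0.42 (shift in favour of TCS): 15.70 / 0.1764 ≈ 89
- 0.18 (shift against TCS): 15.70 / 0.0324 ≈ 485

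**6. Precision if controls are restricted to those able to attend**

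- 21 of 35 able (60%): 1.96 × √(1/22 + 1/21) = 0.598
- 20 v 30 with 10%, 25%, 50% of controls removed (27, 22, 15 left): 0.58, 0.61, 0.67
- 25 v 40 with the same shares removed (36, 30, 20 left): 0.51, 0.53, 0.59

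**The case against.** The strongest reply is that this is an openly non-randomised pilot, not powered for group differences, and that an attendance condition is an ordinary feasibility rule for a six-week workshop. The larger problem is self-selection by interest, which would remain if criterion 4 applied to everyone. That is right, and it limits the weight of this point. It does not remove it, because the effect estimate is meant to inform a larger trial and the missing information is cheap to collect.

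Four stronger readings are tempting, and the documents do not support them.

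- **That controls do include people too ill, busy or remote to attend.** The text permits this but does not show it. Controls are defined by lack of interest, and the recruitment figure, which is not reproduced in the available text, may show where interested but unable people go. The exclusions shared by both arms, "Presence of a life threatening or extreme medical condition" and "Any clinical or cognitive impairment that limits the participant's ability to decide to participate in the study or complete the interviews", narrow the scope for the very ill. Virtual delivery narrows the scope for the remote, though the text does not promise a choice of mode, and the session incentive is handed over at the research centre. Work schedules, and fatigue that allows an interview but not weekly workshops, are not covered.
- **That the difference cannot be removed in analysis.** Too strong. The baseline interview collects health-related quality of life, and the planned instruments cover fatigue and function, so partial proxies should exist. The fair criticism is that no adjustment is planned. Work and transport limits might still go unmeasured.
- **That the bias favours TCS.** The outcome is change, and the sign is not determined (step 4).
- **That the main comparison should be limited to controls able to attend.** This costs precision and leaves controls who could have come but chose not to, which may sharpen the contrast in motivation. It suits a sensitivity analysis better.

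**Conclusion.** The point holds as an unrecorded eligibility asymmetry in a comparison that is already self-selected and is analysed without adjustment. Paired change scores remove stable differences in level, but not differences in trend or regression to the mean.

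The size of any bias cannot be fixed from the documents. On the assumed inputs it runs from negligible (0.04 SD) to more than half the 0.53 SD half-width (0.30 SD), in either direction. Even the largest illustrated value lies inside the planned interval, so this would seldom overturn the pilot's reading by itself. It could, however, move the effect estimate carried into the larger trial. It is worth correcting before recruitment, as a secondary part of the wider self-selection problem.

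**What to change.** - **Record it.** At the screening call, ask every eligible person, whatever their interest, whether they could attend weekly sessions. Record the reason for declining: work, transport, health, or not interested. State in Sampling strategy where a person who is interested but unable to attend goes.
- **Main comparison.** Keep all controls. Adjust the between-group difference in change for the baseline score and for baseline fatigue and function. Confirm that these scales were taken at the last cohort interview: the text says it covers quality of life, but the Table 1 row listing the scales is labelled as follow-up.
- **Sensitivity analysis.** Pre-specify the same comparison restricted to controls able to attend, and report it beside the main one.
- **Interpretation.** State that self-selection by interest remains after both steps, and that the between-group estimate is exploratory.

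The cost is one or two screening questions and a few lines in Data analysis. The main comparison loses no participants. The sensitivity analysis has a wider interval, about 0.60 SD instead of 0.53 SD if 21 of 35 controls could attend. The reasons for declining also serve the stated primary goal of piloting implementation.

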**Data analysis:** Since this is a pilot study the primary focus of the statistical analysis of this study is estimation (effect sizes and associated uncertainty). We will conduct pre- and post-intervention analysis among participants of the intervention group and between group comparisons with intervention and non- intervention groups. Descriptive analyses will be done using frequency distribution and contingency tables for categorical data. Continuous variables will be reported using mean, median, standard deviation, inter-quartile range and range. Chi-square or Fisher's exact test will be done to assess differences in sociodemographic or health indicators between the groups and to compare the independent domains of the quality-of-life scale among patients in the intervention or non-intervention group. To evaluate changes in quality of life before and after the intervention, estimates and 95% confidence intervals will be generated based on the change scores, i.e., using paired data with each subject acting as their own control. Estimates and confidence intervals will be provided for both the individual group changes as well as the difference in change between each pair of groups. We will perform Wilcoxon/Mann-Whitney U-tests (non-parametric) comparing the change scores in each group with each other. These Wilcoxon tests will be performed in addition to a Kruskal-Wallis test (non-parametric ANOVA) in order to test for an overall group effect. The Wilcoxon paired sample test will be used for ordinal data and the Mc Nemar test for significant changes will be used to evaluate dichotomous data. All analyses will be conducted using Stata version 11(Stata Corporation, College Station, Texas, USA).

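### The plan says the pilot will supply adequate data to size a larger study, but the only input it highlights is an effect size too imprecise, and too open to self-selection, for that use

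*Combined protocol and SAP*

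**What the plan says.** The Study design paragraph describes a pilot, non-randomised controlled trial. Sample size determination gives the purpose as "The primary goal of this study is to pilot the potential implementation of this intervention for Long COVID patients" and adds "We are therefore not powering for a definitive assessment of the difference between any two groups". Looking ahead to a bigger trial, it then says "we expect the preliminary data from this study to provide adequate pilot data from which we will be able to determine the required sample size", and continues: "The sample selected will provide an estimate of the effect size and thereby allow preliminary evaluation of the clinical utility associated with the intervention".

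Data analysis says that "the primary focus of the statistical analysis of this study is estimation (effect sizes and associated uncertainty". It plans 95% confidence intervals for change within each group and for the difference in change between groups, with Wilcoxon/Mann-Whitney and Kruskal-Wallis tests. No covariate adjustment is described.

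Sampling strategy expects 20-25 people in the intervention arm, in two or three workshops, and 30-40 in general care. The arms are formed by the participants' own choice: "Those not interested in participating in the intervention will receive general information about chronic disease management available at the CDC website in Spanish".

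No target difference, precision goal, within-person correlation, retention figure or workshop intraclass correlation (ICC) is given for sizing. Four quality-of-life scales are listed and none is singled out.

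**The concern.** A sample size calculation needs a target difference and some nuisance quantities, mainly the SD, the baseline to follow-up correlation, retention and clustering. The plan calls its data adequate for the calculation, yet the quantity it puts forward is the effect size. If the observed effect became the target difference, its error would be magnified, because the required size varies with the inverse square of the effect. A chance overestimate gives a trial too small to detect the true effect. A chance underestimate gives one far too large, or none at all if the sign is negative.

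Self-selection adds to this. People who choose a six-week course may differ from those who decline in motivation, health or available time. An unadjusted contrast carries that difference into the effect estimate, and recruiting more people would not remove it.

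**Working it through.** **Inputs from the documents.** Intervention arm 20-25, general care arm 30-40 (Sampling strategy); 95% intervals on change scores (Data analysis). The plan gives no sample size calculation to reproduce.

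**Assumed, because the documents give none.** True standardised effect δ of 0.2, 0.3 or 0.5 SD; a 1:1 larger trial at two-sided 5% and 80% power; normal approximation; no bias unless stated.

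**Step 1: precision of the pilot effect.** SE = √(1/n₁ + 1/n₂).
- 20 v 30: √(0.0500 + 0.0333) = 0.289; half-width 1.96 × 0.289 = 0.57.
- 22 v 35 (a mid-range case): SE 0.272; half-width 0.53.
- 25 v 40: √(0.0400 + 0.0250) = 0.255; half-width 0.50.

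Workshop clustering in the intervention arm (assumed ICC 0.05, 10 per workshop, design effect 1.45) widens the range to 0.57-0.64.

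**Step 2: what one interval implies.** n per arm = 2(1.96 + 0.8416)²/d². An observed d of 0.3 implies 175 per arm. At 20 v 30 its interval is -0.27 to 0.87: the upper limit implies 21 per arm and the lower limit has the wrong sign. At 25 v 40 it is -0.20 to 0.80: 25 per arm at the upper limit, and again none at the lower. The lower limit is at or below zero for any observed effect up to about 0.50-0.57 SD.

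**Step 3: how often sizing on the estimate works.** The implied n divided by the right n is (δ/d)². Hence:
- n is within ±20% of the right size when d lies between δ/√1.2 and δ/√0.8;
- no size exists when d ≤ 0;
- true power falls below 50% when 2.8016 δ/d < 1.96, that is, d > 1.429 δ.

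Worked case, δ = 0.3 at 22 v 35:
- Within 20%: d from 0.274 to 0.335, z from -0.096 to 0.130, probability 9.0%.
- Zero or negative: z = -0.3/0.272 = -1.10, probability 13.5%.
- True power below 50%: d > 0.429, z = 0.473, probability 31.8%.

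The table gives 22 v 35, with the results at 20 v 30 and 25 v 40 in brackets.

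| True δ | Right n per arm | Within ±20% | Zero or negative | True power < 50% |
|---|---|---|---|---|
| 0.2 | 393 | 6.0% (5.7, 6.4) | 23.1% (24.4, 21.6) | 37.6% (38.3, 36.8) |
| 0.3 | 175 | 9.0% (8.5, 9.6) | 13.5% (14.9, 12.0) | 31.8% (32.8, 30.7) |
| 0.5 | 63 | 14.9% (14.1, 15.9) | 3.3% (4.2, 2.5) | 21.5% (22.9, 20.0) |

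A simulation that also let the pilot SD vary gave nearly the same figures.

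**Step 4: self-selection.** If a true 0.3 SD is inflated by an assumed 0.1 or 0.2 SD, the apparent 0.4 or 0.5 gives 99 or 63 per arm instead of 175. True power is then Φ(0.3/√(2/99) - 1.96) = 56% or Φ(0.3/√(2/63) - 1.96) = 39%.

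**Step 5: what the pilot can supply.** With df = n₁ + n₂ - 2, the 95% CI for an SD is √(df/χ²) at the two tail points. That is 0.83-1.25 times the estimate at 20 + 30, and 0.85-1.21 times at 25 + 40. In sample size terms the factors are 0.70-1.56 and 0.73-1.47. Using the one-sided 80% upper limit of the SD raises n by about 1.21 or 1.18, so 175 becomes about 212 or 207.

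**Recruitment figures.** Sampling strategy also says that 20-25 people will be identified in all and that about half will want the intervention. That conflicts with 50-65 across the two arms and must be reconciled. With only 20-25 in total, split evenly, the half-width is about 0.88 (10 v 10) to 0.78 (12 v 13).

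**The case against.** The strongest reply is that the plan never says the observed effect will be the target difference. The sizing sentence speaks of preliminary data, and the sentence on effect size links it to clinical utility. A reader might infer that the sponsor has committed to sizing on the point estimate; the text does not go that far. What stands is that effect size is the only input put forward and the method is left open, while the data are already described as adequate.

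The plan also disclaims power and promises confidence intervals. That is a fair defence of the pilot as an estimation study. It does not rescue the sizing claim, because over the plausible range of observed effects the interval spans a small trial and no trial at all.

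Three other strong readings fail:
- That the useful pilot quantities are missing altogether. Data analysis does report standard deviations and paired changes, and the Reaction level under Specific Aim 2 uses the attendance items of the final TCS form. Uptake, retention and the correlation are what the analysis lacks.
- That a follow-on trial being too small about half the time shows imprecision. Any unbiased, symmetric estimate exceeds the truth half the time at any sample size. The informative figures are how far the size misses.
- That sizing is the study's main product. The stated primary goal is to pilot implementation.

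**Conclusion.** The point holds as a mismatch between a stated property and the design: adequacy for sizing is asserted, and the effect estimate cannot provide it. At the planned arm sizes, sizing on the pilot effect would miss the right number by more than 20% in roughly 84-94% of pilots for true effects of 0.2 to 0.5 SD, before any selection bias. The true effects, the larger trial's error rates, the bias values and the ICC are assumptions. The conclusion is the same across the range of effects shown, though the chance of a zero or negative estimate depends strongly on the effect assumed.

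A reader might infer that the pilot is useless for planning. It is not: the SD can be estimated well enough to use with an upper confidence limit, and attendance, uptake and retention can be estimated too. The criticism applies to using the effect estimate as the target. No participant is put at risk, but the sponsor should correct the claim before a larger study relies on it.

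**What to change.** Rewrite the last two sentences of Sample size determination to say that:
- the larger trial will be sized on a minimally important difference, stated in advance, for one quality-of-life outcome that the sponsor names now. EQ-5D-5L is one candidate, provided its summary score is defined; the choice is the sponsor's;
- the pilot effect will be reported with its 95% CI but will not serve as the target difference;
- the pilot will supply the SD of the outcome or of its change (at an upper confidence limit), the baseline to follow-up correlation, and session attendance from the final TCS form;
- two or three workshops cannot estimate the workshop ICC, which must come from elsewhere.

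Add to Data analysis the uptake (accepted out of invited) and the follow-up retention, each with a 95% CI. This requires a count of those invited to be kept.

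The cost is about a paragraph of text and two short additions to the analysis; the outcome data are already planned. The minimally important difference has to be justified from an outside source, and the pilot will claim less about efficacy.
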